1.1 Title and trial registration

A randomized, parallel-group treatment, participant, investigator, care provider and outcomes assessor masked, two-arm study to assess the effectiveness of cod liver oil compared to placebo in the prevention of COVID-19 and airway infections in healthy adults

Short: Cod Liver Oil for COVID-19 Prevention (CLOC) Study

1.2 SAP version

SAP version 1.0 - 23-November-2021

1.3 Protocol version

Cod Liver Oil for C-19 Prevention Study, protocol version 1.02, November 10, 2021

1.4 SAP revisions

Version No. – Date	Justification	
0.1 – 3-Jun-2021	Initial draft	Pre-analysis
0.9 – 12-Aug-2021	Second draft	Pre-analysis
0.99 – 24-Aug-2021	Draft for approval	Pre-analysis
1.0 – 24-Nov-2021	SAP approved	Pre-analysis
1.1 – 10. Des-2021	Amendment 1	Pre-analysis

Amendment 1 (December 10, 2021)

Added the time period 'from one week after the start of cod liver/placebo taking to the end of the study period' to primary endpoint 1-4 in accordance to the protocol.

2.1 Background and rationale

Preliminary evidence from literature and an ongoing study (the Norwegian Corona Cohort, Koronastudien) in our lab suggests that cod liver oil may prevent COVID-19 and complications of COVID-19. In this Cod Liver Oil for COVID-19 Prevention (CLOC) study, we will investigate whether this is actually the case by randomizing volunteers to take cod liver oil or placebo (corn oil) during the winter months of 2020-2021.

2.2 Objectives

Based on the encouraging results from Koronastudien¹ as well as existing evidence from the literature, we aim to investigate whether cod liver oil can prevent COVID-19, serious COVID-19, or other airway infections.

Adverse events will also be presented.

We also aim to explore and confirm already known health effects and possible new health effects in particular rare adverse events associated with cod liver oil use. This will be done during a follow-up period of up to two years after the end of the cod liver oil period.

3. Study Methods

3.1 Trial design

The CLOC study aim to include 80,000 participants that will be randomized in a 1:1 ratio to consume 5 ml cod liver oil or placebo (corn oil) with lemon taste per day for 6 months.

The study was organized as an ancillary study of Koronastudien, a cohort study that aims to identify risk factors associated with the community- and workplace acquisition of COVID-19 virus and which also aims to identify risk factors for the progression of the

¹ In Koronastudien, the Norwegian Corona Cohort, 140.000 participants have answered a questionnaire about their use of dietary supplements, demographics, airway symptoms, and risk factors for Covid-19. In univariate analyses, it was found that participants using vitamin D and or cod liver oil were associated with a reduced risk of Covid-19 (OR 0.8, p<0.001) and of serious (hospitalized) Covid-19 with hospitalization (OR 0.3, p=0.07).

disease and to understand the virus and the disease itself. Koronastudien has collected extensive electronic questionnaire data using the University of Oslo web-based solution "Nettskjema". Participants of the CLOC study will be a subgroup of participants in Koronastudien, and relevant data from these participants will be shared among the studies.

The hypotheses are:

Intake of cod liver oil can prevent COVID-19 disease

Intake of cod liver oil can prevent serious COVID-19

Intake of cod liver oil can prevent other airway infections

These hypotheses will be tested in a triple-blinded randomized placebo-controlled study where 80.000 participants will be assigned to cod liver oil or placebo in a 1:1 ratio.

The safety of cod liver oil will be explored.

Finally, it is a separate aim of the study to identify the mechanisms of action of any health effects seen. These will be explored under another SAP.

3.2 Randomization

Willing and eligible participants will be randomly assigned to one of two treatment groups: 5 ml of cod liver oil x1 per day or placebo together with the first meal each day. Participants will be assigned to the cod liver oil or placebo group in a 1:1 ratio.

Concealment of allocation: Randomization will be conducted at the Department of Research Support, Oslo University Hospital, by personnel not involved in the study. The list of participants with address and treatment assignment will be provided to the packaging company, which will send cod liver oil or placebo for the whole study period to each participant based on that list. The responsible personnel at the packaging company will not be involved in the study, and no personnel involved in the study will have access to this list.

The number of participants to be randomized: In the case of successful recruitment of an excess number of participants, participants belonging to high-risk groups (> 70 years old and dark-skinned) will be prioritized for randomization. The remaining non-randomized participants will be included as an extra control group that will not receive any treatment but will otherwise be followed as the other participants and analysed for the exploratory endpoints.

Previous use of vitamin D

Caucasians using cod liver oil or an equivalent supplement (containing vitamin D) less frequently than 5 days per week can be included in the study. In addition, dark-skinned individuals may be included regardless of previous use of vitamin D (and cod liver oil). We consider the risk of overdosing of vitamin D to be very low in this group and while the group will contribute less to the total power of the study than participants not using such supplements their intake will increase during the study period and they will contribute to the study. Based on data from Koronastudien we expect less than 20-30% such participants.

3.3 Sample size

The fallback method (<https://www.fda.gov/media/102657/download>) will be used to correct for testing of multiple primary endpoints.

The total alpha (0.05) will be divided among the endpoints, and a fixed sequence for the testing will be maintained. As the testing sequence progresses, a successful test preserves its assigned alpha as "saved" (unused) alpha that is passed along to the next

test in the sequence. This passed-along alpha is added to the assigned alpha of the next endpoint, and the summed alpha is used for testing that endpoint. Thus, as sequential tests are successful, the alpha accumulates for the endpoints later in the sequence; these endpoints are then tested with progressively larger alphas.

Endpoints in testing order with power calculation:

1. Serious COVID-19 (MSIS-confirmed COVID-19 with dyspnoea, hospitalization, or death). (MSIS: Mandatory Norwegian Surveillance System for Communicable Diseases). Assigned $\alpha=0.018$.

Based on the observations in Koronastudien of a 40% reduction in serious COVID-19 in the group reporting use of cod liver oil, and an expected incidence of 0.25%, a power of 70%, 67,000 participants will have to be included for this endpoint.

2. COVID-19 positive PCR (MSIS). Assigned $\alpha=0.03$.

Based on the observations in Koronastudien of a 20% reduction in COVID-19 incidence in the group reporting use of cod liver oil, and an expected incidence of 1%, a power of 70%, 65,000 participants will have to be included for this endpoint.

3. A negative SARS-CoV-2 test (MSIS). Assigned $\alpha=0.001$.

COVID tests (SARS-CoV2-2), real time (RT)-PCR, are mostly obtained because of a suspicion of COVID-19. The number of negative COVID tests from one week after starting taking cod liver oil/placebo and to the end of the intervention period. This endpoint has been added as an alternative to the Positive PCR or bacterial culture endpoint (now a secondary endpoint, as it is not available at this time).

4. Self-reported airway infection. Assigned $\alpha=0.001$.

Based on the expected frequency of airway infections in Koronastudien of >30% and as a threshold of clinically interesting reduction of all airway infections of 10%, 23,000 participants will have to be included for this endpoint. The study has a power for this endpoint >95%. 16,000 participants in the study will give an 80% power for this endpoint.

The power of the study is dramatically influenced by the incidence of COVID-19, and this will be considered when the statistical analysis plan is finalized before unblinding to maximize the scientific output of the study. Thus, the statistical analyses including p-values and testing-order above can be changed if the COVID-19 situation dictates such changes. Any change will be done before unblinding. The time of unblinding can be changed based on the prevalence of COVID-19 to increase the scientific output from the study.

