4.1 Confidence intervals and *P* values

An overall significance level of 0.05 is used for the composite primary endpoints and are tested in the specified order as seen in section 3.3, above. To control the overall significance level pertaining to the primary hypotheses, the fallback method for alpha spending is used for the statistical analyses of relative risk comparing the two randomisation groups, Cod liver oil and Corn oil. If the first analysis results in significant results, i.e., $p \leq 0.018$, according to section 3.3, the second null-hypothesis can be tested at a significance level of $0.018 + 0.030 = 0.048$. If the first null hypothesis is not rejected, the second is tested at the stated significance level of 0.03. Each following null hypothesis to be tested has a significance level of its stated level plus the sum of the levels of previous tests that result in a significant result. Supplementary analyses, such as regression analyses, will not be part of the fallback method, as these are expected to be highly correlated to the primary analyses. Confidence interval and p-values will be provided for all variables tested statistically.

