The handling data will be closely connected to the handling of data in Koronastudien, and for data handling purposes, the CLOC study will be treated as a sub-study of Koronastudien. An application to process and store data from the two studies together will be sent to the Data Protection Officer at Oslo University Hospital. Koronastudien has been approved by the Data Protection Officer at Oslo University Hospital in accordance with the European GDPR regulations.

The University of Oslo service for sensitive data (TSD) will be used to collect, store, and analyze data. Additionally, HUNT cloud and LEDIDI Prjcts will be used for analyzing data. The data will be analyzed without any directly personally identifying information using a Study ID instead. The patient list connecting the patient identity with the study ID will be kept in a separate folder in TSD, and the backup will be kept at an encrypted USB data storage device. Deidentified data will be backed up at K:/sensitive, a secure location at the Oslo University Hospital's internal web.

9. Statistical considerations

The detailed statistical analysis plan will be approved by the study steering committee before unblinding.

Statistical Hypotheses

See Sample Size Determination and the statistical analysis plan

Sample Size Determination

The fallback method (https://www.fda.gov/media/102657/download) will be used to correct for testing of multiple primary endpoints.

The total alpha (0.05) will be divided among the endpoints, and a fixed sequence for the testing will be maintained. As the testing sequence progresses, a successful test preserves its assigned alpha as "saved" (unused) alpha that is passed along to the next test in the sequence. This passed-along alpha is added to the assigned alpha of the next endpoint, and the summed alpha is used for testing that endpoint. Thus, as sequential tests are successful, the alpha accumulates for the endpoints later in the sequence; these endpoints are then tested with progressively larger alphas.

Endpoints in testing order with power calculation:

1. Serious Covid-19 (Covid-19 with self-reported dyspnea, self-reported hospitalization, or death). Assigned α =0.018.

Based on the observations in Koronastudien of a 40% reduction in serious Covid-19 in the group reporting use of cod liver oil, and an expected incidence of 0.25%, a power of 70%, 67,000 participants will have to be included for this endpoint.

- Covid-19 positive PCR. Assigned α=0.03.

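### The forwards-only fallback is valid but leaves alpha unused: an arrow from endpoint 4 back to endpoint 1 would raise endpoint 1's power by about 1 to 8 points, within the 0.05 family-wise bound

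*SAP*

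**What the plan says.** SAP 3.3 sets the frame: "The total alpha (0.05) will be divided among the endpoints, and a fixed sequence for the testing will be maintained". The split is 0.018 for serious COVID-19 (endpoint 1), 0.03 for a positive PCR (endpoint 2), 0.001 for negative SARS-CoV-2 tests (endpoint 3) and 0.001 for self-reported airway infection (endpoint 4). A successful test hands its alpha on: "This passed-along alpha is added to the assigned alpha of the next endpoint, and the summed alpha is used for testing that endpoint". As a result "the alpha accumulates for the endpoints later in the sequence; these endpoints are then tested with progressively larger alphas".

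SAP 4.1 tests endpoint 1 at 0.018 and endpoint 2 at 0.048 if endpoint 1 succeeds. Otherwise, "If the first null hypothesis is not rejected, the second is tested at the stated significance level of 0.03". Its last rule gives each later hypothesis its own level plus the levels of all earlier significant tests.

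Protocol section 9 (Sample Size Determination) repeats the 3.3 scheme and says that "a fixed sequence for the testing will be maintained". Neither document returns alpha to an earlier endpoint. Both allow changes to significance levels and testing order before unblinding, if the COVID-19 situation requires them.

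**The concern.** Suppose endpoint 1 misses 0.018 and endpoints 2, 3 and 4 then succeed. Under 3.3 they are tested at 0.030, 0.031 and 0.032. After the last success, 0.032 has no hypothesis left to go to, while endpoint 1 is still open. It is the sponsor's first question, with the lowest expected incidence (0.25%) and planned power of 70%.

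The order of testing and the split of alpha are legitimate choices and are not at issue. The question is whether the unused alpha can go back to endpoint 1 without breaking the 0.05 bound, and how much power that buys.

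**Working it through.** **1. Reproduce the plan's sample size.** Inputs from SAP 3.3: 0.25% against 0.15% (40% reduction), alpha 0.018, power 70%, 1:1 allocation. Sidedness is not stated; two-sided is assumed because it reproduces the figure.

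n per arm = [z(1−α/2)·√(2p̄(1−p̄)) + z(power)·√(p₁(1−p₁)+p₂(1−p₂))]² / (p₁−p₂)²

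With p̄ = 0.002, z = 2.3656 and 0.5244, and square roots 0.06318 and 0.06318, the total is 66,684, against 67,000 stated. A one-sided test gives 54,860 and a continuity correction 70,626, so neither fits. Endpoint 2 (1% against 0.8%, alpha 0.03) gives 64,754 against 65,000. The alphas sum to 0.05.

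**2. Levels for endpoint 1 with a return arrow.** Each rejected endpoint passes its whole current level to the next unrejected one, in the cycle 1→2→3→4→1.
- Endpoint 4 fails: 0.018.
- Endpoint 4 succeeds and endpoint 3 does not: 0.018 + 0.001 = 0.019.
- Endpoints 3 and 4 succeed, 2 does not: 0.018 + 0.002 = 0.020.
- Endpoints 2, 3 and 4 succeed: 0.018 + 0.032 = 0.05.

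**3. Error control.** Write each scheme as a closed test with Bonferroni weights on all 15 intersections. The eight that contain endpoint 4 already sum to 0.05 and do not change. The other seven do:

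| Intersection | Weights, SAP 3.3 | Sum | Weights, with arrow | Sum |
|---|---|---|---|---|
| 1 | 0.018 | 0.018 | 0.05 | 0.05 |
| 2 | 0.048 | 0.048 | 0.05 | 0.05 |
| 3 | 0.049 | 0.049 | 0.05 | 0.05 |
| 1, 2 | 0.018, 0.030 | 0.048 | 0.020, 0.030 | 0.05 |
| 1, 3 | 0.018, 0.031 | 0.049 | 0.019, 0.031 | 0.05 |
| 2, 3 | 0.048, 0.001 | 0.049 | 0.049, 0.001 | 0.05 |
| 1, 2, 3 | 0.018, 0.030, 0.001 | 0.049 | 0.019, 0.030, 0.001 | 0.05 |

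Every sum is 0.05 with the arrow, so strong control holds whatever the correlation between endpoints. No weight is smaller than under 3.3, so no rejection under 3.3 is lost.

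**4. Endpoint 1 power at each level** (same formula, solved for power):

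| N | 0.018 | 0.019 | 0.020 | 0.05 |
|---|---|---|---|---|
| 67,000 | 70.2% | 70.9% | 71.6% | 82.6% |
| 80,000 | 78.8% | 79.4% | 79.9% | 88.6% |

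**5. Overall power with the arrow,** endpoints independent. Endpoint 2's power at 0.03 is 71.6% at 67,000 and 79.5% at 80,000. Endpoint 4's power at 0.001 (30% against 27%) is practically 100% at both sizes. Endpoint 3 has no stated power, so its power at level 0.031 is varied.

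For 90% at 67,000: P(2 and 3 succeed) = 0.716 × 0.9 = 0.644. P(3 succeeds at 0.001 and 2 fails) = 0.559 × 0.284 = 0.159. The remainder is 0.197. Power = 0.644 × 82.6% + 0.159 × 71.6% + 0.197 × 70.9% = 78.5%.

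| Endpoint 3 | 67,000 | 80,000 |
|---|---|---|
| no effect | 70.2% → 71.2% | 78.8% → 79.6% |
| power 50% | 70.2% → 75.1% | 78.8% → 83.1% |
| power 90% | 70.2% → 78.5% | 78.8% → 86.0% |

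Serious cases are a subset of all cases, so endpoints 1 and 2 are correlated. With √(0.2%/0.9%) = 0.47, taken from the average incidences, simulation gives gains of 0.9 to 7.1 points at 67,000 and 0.8 to 6.1 at 80,000.

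**6. The last rule in 4.1, read literally.** Assume independent tests.
- Endpoint 1 has an effect and is rejected; the other three are null. Endpoint 2 is tested at 0.048, and endpoints 3 and 4 at 0.019 each when those before them fail. Family-wise error = 1 − 0.952 × 0.981 × 0.981 = 0.084.
- Endpoints 1 and 2 are rejected; 3 and 4 are null. Each is tested at 0.049 or more. Error = 1 − 0.951 × 0.951 = 0.096.

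**The case against.** The plan names a recognised method and, as described in 3.3, the method holds 0.05. Preferring another valid procedure does not make this one wrong. That stands: this is an efficiency point, and a reader who infers that the fallback in 3.3 is invalid goes beyond the documents.

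Three further readings are tempting and also too strong.
- *Endpoint 1's power goes from 70% to 83%.* That holds only when endpoints 2, 3 and 4 all succeed. The 70% also belongs to 67,000; at the planned 80,000 it is 79% with no change.
- *Putting the best-powered endpoint last wastes the alpha.* Endpoint 4 owns 0.001, and its success alone lifts endpoint 1 to 0.019. Nearly all of the 0.032 is endpoint 2's 0.03, which returns only through successes on 2, 3 and 4.
- *The change has no error cost of any kind.* The family-wise bound is kept, but if endpoint 1 is the only true null, its false-positive rate can rise from 0.018 towards 0.05. At the stated effects and 67,000 it would be about 0.020 to 0.039 (for example 0.644 × 0.05 + 0.159 × 0.020 + 0.197 × 0.019 = 0.039). A sponsor may prefer the stricter level for its most serious endpoint and can say so.

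It is also fair to object that some rejections possible under the literal last rule of 4.1 would disappear. For example, endpoint 3 could be tested at 0.019 after endpoint 1 succeeds and endpoint 2 fails, against 0.001 under the graph. Those rejections are not validly controlled, so losing them is a correction.

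**Conclusion.** The point holds as an available improvement. The scheme in SAP 3.3 controls family-wise error at 0.05 but is uniformly dominated by the same weights and order with a return arrow. The overall gain for endpoint 1 is about 1 to 8 points at 67,000 and 1 to 7 at 80,000, slightly less with correlation between endpoints 1 and 2.

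The validity result is exact and needs no assumption about correlation. The size of the gain rests on the plan's own effects and incidences, two-sided tests, and an assumed power for endpoint 3. If endpoint 3 has little effect, the gain is about one point.

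The literal last rule of 4.1 is the more serious matter in this part of the plan. It conflicts with 3.3 and can take family-wise error to 0.084 or 0.096. It must be replaced whether or not the arrow is adopted.

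**What to change.** Before unblinding, replace the verbal rules in SAP 3.3 and 4.1 and the matching text in protocol section 9 with one graphical procedure:
- initial levels 0.018, 0.03, 0.001 and 0.001, in the present order;
- each rejected endpoint passes its whole current level to the next unrejected endpoint, with arrows updated after every rejection;
- an arrow from endpoint 4 back to endpoint 1;
- nothing passes from an endpoint that has not been rejected, which removes the last rule of 4.1.

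State the levels for endpoint 1 (0.018, 0.019, 0.020 or 0.05) and that tests are two-sided, if that is intended.

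The cost is a few lines of text, an SAP amendment and a matching protocol amendment, with no extra participants or data. The SAP is already approved, and section 3.6 has the primary analyses follow at once, so the time for this is short. The documents do not show when unblinding takes place. If it has already happened, the return arrow should not be added, and the primary tests should follow the carry rule in 3.3, not the literal rule in 4.1.

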3.4 Framework

The background for the study is that data suggest that cod liver oil may prevent COVID-19 and complications of COVID-19. Hence, this is a superiority study, placebo-controlled, blinded and randomised, designed to show that cod liver oil has a positive effect on COVID-19 and complications of COVID-19, compared to corn oil, the placebo.

3.5 Statistical interim analyses and stopping guidance

No interim analyses were planned in this study. The study's duration has been specified to last during the winter months of 2020–2021, with a duration from 1–6+ months for the participants.

3.6 Timing of final analysis
All primary variables will be analysed after ending the intervention part of the present study. Analyses of the four primary variables will be conducted immediately pursuant to the approval of this SAP. Further analysis of the secondary variables will be specified in another SAP.

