C) death where the Covid-19 infection was wholly or partly responsible as judged by the death certificate, information from relatives or hospital records (see endpoint in the protocol)

B. Number of participants diagnosed with New Covid-19 (primary endpoint):

The number of participants diagnosed with first time SARS-CoV-2 positive nasopharyngeal and or pharyngeal swabs (or any other sample used for detection of current disease) analyzed by reverse transcriptase quantitative polymerase chain reaction (RT-qPCR) nucleic acid amplification test or antigen tests used by accredited Norwegian microbiology laboratories from one week after the start of cod liver oil/placebo taking.

C. A negative SARS-CoV-2 test (primary endpoint)

Covid tests (SARS-CoV-2), real time (RT)-PCR, are mostly obtained because of a suspicion of COVID-19. The number of negative covid tests from one week after starting taking cod liver oil/placebo and to the end of the intervention period. This endpoint has been added as an alternative to the Positive PCR or bacterial culture endpoint (below, secondary endpoint, which is not available at this time).

D. Number of participants with self-reported airway infection (primary endpoint)

The number of self-reported airway infections in the period from one week after starting taking cod liver oil/placebo to the end of the intervention period.

Secondary endpoints

The testing of secondary endpoints will be described in the Statistical Analysis Plan.

- A) Hospitalization for Covid-19
- B) ICU care for Covid-19
- C) Any admissions to hospital
- D) Infection with each of the mentioned pathogens
- E) Visits at GP for infections
- F) Visits at GP
- G) Laboratory confirmed respiratory tract infection (previous primary endpoint)

G) Number of participants with laboratory confirmed respiratory tract infection (this is a previous primary endpoint, which will be studied later when data from laboratories are available):

An airway sample positive for a respiratory pathogen* (either PCR or culture) in the period from one week after the start of cod liver oil/placebo taking to the end of this period

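### SAP 3.6 defers the secondary endpoints to an undated second SAP, and nothing ensures that it is approved before unblinding

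*SAP*

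**What the plan says.** SAP section 3.6 makes two statements in succession. On the primary endpoints: "Analyses of the four primary variables will be conducted immediately pursuant to the approval of this SAP". On the others: "Further analysis of the secondary variables will be specified in another SAP". It gives the other SAP no date or version, and no condition tied to unblinding.

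The protocol makes two commitments. Section 3, under the secondary endpoints: "The testing of secondary endpoints will be described in the Statistical Analysis Plan". Section 9, in its opening line: "The detailed statistical analysis plan will be approved by the study steering committee before unblinding".

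The protocol's secondary list runs from A to G: hospitalisation for COVID-19, intensive care for COVID-19, any hospital admission, infection with each listed pathogen, GP visits for infection, all GP visits, and laboratory-confirmed respiratory infection. The last of these was a primary endpoint before the current protocol version.

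**The concern.** Read together, the protocol's two commitments mean that secondary tests are fixed while the trial is still blinded. SAP 3.6 separates them from the document that carries that protection and does not carry the protection over to the new one. The primary analyses compare the randomised groups (SAP 4.1). If the steps are taken in the order written, the between-group primary results could be known while the secondary analyses are still open.

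What is at stake is the standing of the secondary results. Several are close relatives of the primary endpoints: hospitalisation for COVID-19 is a component of the first primary endpoint, and G is a former primary. If their test, data source or order could have been chosen with the primary results in hand, a reader cannot tell a planned finding from a selected one.

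**Working it through.** The plan states no figure for this point, so the check is mainly a comparison of text.

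1. **What the protocol requires.** Secondary testing belongs in the SAP (section 3), and the SAP is approved before unblinding (section 9). It follows that secondary testing is to be fixed before unblinding.

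2. **What the SAP contains.** Sections 6.1 to 6.3 define outcomes, methods and missing-data handling for the four primary variables. Nowhere does the SAP list the secondary endpoints or give a test or a multiplicity rule for them.

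3. **Whether another rule closes the gap.** SAP 3.3 says "Any change will be done before unblinding", but this concerns changes to the analyses and testing order set out there for the primary endpoints. It does not bind a document still to be written. The revision table in SAP 1.4 labels each version as pre-analysis, which is not the same as pre-unblinding, and lists no second SAP. SAP 6.2 allows further subgroup work prompted by the primary findings, so analysis informed by results is already foreseen.

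4. **What remains open.**
 - For A to G: the test, the order and the multiplicity handling.
 - For A: the data source as well. The primary component uses self-reported hospitalisation (protocol section 3; SAP Appendix 1). Protocol section 8 describes patient-registry diagnoses checked against hospital records. The secondary list does not say which applies.
 - For D: the number of tests. The pathogen list has 14 entries and may be extended.

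5. **Alpha.** The primary levels are 0.018, 0.03, 0.001 and 0.001 (SAP 3.3). Their sum is 0.018 + 0.03 + 0.001 + 0.001 = 0.05, the whole of the stated total. The fallback rule in SAP 4.1 passes alpha only along these four tests, so neither document assigns any to the secondaries.

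6. **Dates.** The revision table dates approval to 24 November 2021 and Amendment 1 to 10 December 2021, still labelled pre-analysis. The interval is 6 days to the end of November plus 10 in December, which is 16 days.

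7. **An illustration of multiplicity only.** Seven independent tests at 0.05 with no true effect give 1 − 0.95^7 = 0.302, about 30%, as the chance of at least one false positive. The figure would be the same had the seven tests been written before unblinding, so it does not measure the timing problem. Independence is also implausible, because GP visits for infection are contained in all GP visits and the pathogens in D largely make up G.

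**The case against.** A reader might infer that the secondary tests *will* be specified after unblinding, in breach of the protocol. The documents do not support that.

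- Neither unblinding nor the second SAP has a calendar date. Protocol section 3 equates unblinding with the end of oil intake when it describes the six-month endpoints, but section 9 lets the time be moved.
- The 16 days between approval and a pre-analysis amendment show that the primary analysis did not follow approval at once. A second SAP could have been approved in that interval or before; the documents neither show nor exclude it.
- Dividing the analysis plan by topic is not a breach in itself. SAP 3.1 does the same for mechanisms of action. A separate secondary SAP approved before unblinding would meet the protocol's purpose.

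Three further points also stand. D and G already have protocol definitions (sample, method, pathogen list and, for G, time window), so it would be wrong to say that every definition is open. COVID-19 hospital diagnoses taken from registries have a blinded second review in protocol section 8. And SAP 4.1 limits control of the overall significance level to the primary hypotheses, so no confirmatory secondary claim is promised.

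Two counter-arguments do not remove the point. First, G is an endpoint "which will be studied later when data from laboratories are available". Late data explain a late analysis but not the lack of a prespecified test, and the remark does not cover A, B, C, E or F. Second, it may be said that secondary endpoints are exploratory anyway. Neither document says so, and protocol section 3 lists exploratory endpoints under their own heading.

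**Conclusion.** The point holds as a missing safeguard. SAP 3.6 starts the between-group primary analysis on approval and sends all seven lettered secondary endpoints to an undated document, with no requirement that it precede unblinding. The protocol's commitments imply that requirement, and the current SAP does not secure it.

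The consequence is confined to the secondary results. The four primary tests, their alpha and their order are unaffected. The documents do not allow the effect to be expressed as an error rate, and the 30% above should not be used for that purpose.

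The conclusion assumes that whoever writes the second SAP could see the primary results; the documents do not say who that is. It does not assume that the codes were in fact opened first.

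**What to change.** Add to SAP 3.6 that any secondary endpoint whose analysis is not specified in a SAP approved and dated before the treatment codes are opened will be reported as exploratory, with no confirmatory claim. This costs one sentence, does not hold up the primary analyses, and remains valid if the codes have already been opened.

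Preferably, also approve the second SAP before unblinding. For A to G it should give the data source (self-report or registry for hospitalisation), the test, the order and the multiplicity handling, including how many pathogen tests D involves. Because all 0.05 is assigned to the primaries, it should also say on what basis any secondary test would be judged. The cost is a possible delay to opening the codes, whose length cannot be judged from the documents. Endpoint G can have its test fixed now and be analysed when the laboratory data arrive.
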